5.2 Exclusion Criteria

Subjects who meet any of the following criteria will not qualify for the study.

1. Any concomitant disease or disorder that has symptoms of spasticity or that may influence the subject's level of spasticity.
2. Inability to rate their level of spasticity or distinguish it from other MS symptoms.
3. Use of high dose oral or intravenous methylprednisolone, or equivalent, within 3 months before Baseline.
4. History of allergy to baclofen or any inactive components of the test formulation.
5. Concomitant use of medications that would potentially interfere with the actions of the study medication or outcome variables (Appendix 5).
6. Pregnancy, lactation, or planned pregnancy during the course of the study and for 3 months after the final study visit.
7. Recent history (within past 12 months) of any unstable psychiatric disease (or yes response to questions 1 or 2 on the Columbia Suicide Severity Rating Scale [C-SSRS] at baseline), or current signs and symptoms of significant medical disorders such as severe, progressive,

^b GFR Calculator:

$GFR \text{ (mL/min/1.73 m}^2\text{)} = 175 \times (\text{Scr (mg/dL)})^{-1.154} \times (\text{Age (years)})^{-0.203} \times (0.742 \text{ if female}) \times (1.212 \text{ if African American})$ (conventional units)

$GFR \text{ (mL/min/1.73 m}^2\text{)} = 175 \times (\text{Scr } (\mu\text{mol/L})/88.4)^{-1.154} \times (\text{Age (years)})^{-0.203} \times (0.742 \text{ if female}) \times (1.212 \text{ if African American})$ (SI units)

or uncontrolled pulmonary, cardiac, gastrointestinal, hepatic, renal, genitourinary, hematological, endocrine, immunologic, or neurological disease.

8. History of epilepsy.
9. Current significant cognitive deficit, severe or untreated anxiety, severe or untreated depression.
10. Subjects with abnormal micturition that requires indwelling or intermittent catheterization or with lower urinary tract symptoms (LUTS) that result in a score >26 in the Baseline Urinary Symptom Profile – USP[®] (USP) questionnaire (Appendix 6). Subjects who are proficient in self-catheterization may be included in the study at the investigator's discretion.
11. Current malignancy or history of malignancy that has not been in remission for more than 5 years, except effectively treated basal cell skin carcinoma.
12. Subject has clinically significant abnormal laboratory values, in the opinion of the investigator at Screening (at Visit 6 for rollover subjects).
13. Any other significant disease, disorder, or significant laboratory finding, including clinically significant abnormal laboratory values or ongoing serious adverse events (SAEs) at Visit 6 (Final Visit) of Study OS440-3004, which, in the opinion of the investigator, puts the subject at risk because of participation, influences the result of the study, or affects the subject's ability to participate.
14. Planned elective surgery or other procedures requiring general anesthesia during the course of the study.
15. History of any illicit substance abuse (e.g., alcohol, marijuana, cocaine) or prescription for long-acting opioids within the past 12 months (tramadol use will be allowed).
16. Participation in another clinical research study (with the exception of Study OS440-3004) within 1 month of Baseline.

6 STUDY PROCEDURES

Table 1 and the following subsections present the planned study visits, timing, and details for study procedures. Figure 1 presents the timeline diagram for the study. The flowchart depicting the open-label dosing schema for this study is presented in Figure 2.

Table 1: Schedule of Assessments, Study OS440-3005

Assessment or Procedure	Screening ¹	Baseline ¹	Baseline ¹	Visits							Final Visit ²
	De Novo subjects only	De Novo subjects only	(V6 of prior DB Study)	1	2	3	4	5	6 ⁶	7 (telephone visit)	8
Study Week	up to 21 days before Baseline	0 (±3 days)	0 (±3 days)	2 (±3 days)	6 (±5 days)	14 (±5 days)	28 (±5 days)	42 (±5 days)	54 (±3 days)	56 (±5 days)	60 (±3 days)
Written informed consent	X		X								
Inclusion and exclusion criteria	X		X								
Withdrawal anti-spasticity medication	X		X								
Assign enrollment number		X	X								
Demography	X		X								
Medical/surgical history; physical examination; height	X		X								
Weight	X		X				X				X
Vital signs ³	X	X	X	X	X	X	X	X	X		X
Hematology/serum chemistry/urinalysis	X		X		X	X	X	X	X		X
Electrocardiogram	X		X				X				X
Pregnancy test ⁴	X	X	X	X	X	X	X	X	X		X
C-SSRS	X	X	X	X	X	X	X	X	X		X
TNmAS-MAL ⁵	X	X	X				X				X
EDSS	X		X				X				X
PGIC		X	X								X
USP [®] questionnaire	X	X	X	X	X	X	X	X	X		X
Dispense study medication		X	X	X	X	X	X	X	X ⁶		
Collect unused study medication				X	X	X	X	X	X		X
Adverse event assessment		X	X	X	X	X	X	X	X	X	X
Concomitant medications/therapies	X	X	X	X	X	X	X	X	X	X	X
Schedule/confirm next study visit		X	X	X	X	X	X	X	X	X	

C-SSRS = Columbia–Suicide Severity Rating Scale; DB = double-blind; EDSS = Expanded Disability Status Scale; FV = final visit; PGIC = Patient Global Impression of Change; TNmAS-MAL = Total Numeric-transformed modified Ashworth Scale score of the most affected limb; USP = Urinary Symptom Profile (footnotes on next page)

[figure not shown]
Table 1 - Footnotes:

1. Baseline for the study will be conducted at the same time as Visit 6/Day 92 (Final Visit) of Study OS440-3004 for subjects willing to continue into this study. All assessments performed at Visit 6/Day 92 (Final Visit) of Study OS440-3004 should not be repeated but should be recorded as the same assessments at Baseline for this study.

Note: For *de novo* subjects being considered for enrollment, a Screening visit should occur a maximum of 21 days prior to Baseline to allow for any concomitant medication wash-out required for Inclusion Criterion 6. For *de novo* subjects, only the following assessments and procedures will be performed at the Baseline visit: assign enrollment number, vital signs, urine pregnancy test, C-SSRS, TNmAS-MAL, PGIC, USP, dispensing of study medication, recording of AEs and concomitant medications, and scheduling/confirmation of the next study visit.

2. If a subject prematurely withdraws from the study, the subject should taper from study medication as described in Section 7.1 and all evaluations described under Visit 8/Week 60 (Final Visit) must be performed.
3. Vital signs will be measured with the subject in a supine position and in a standing position 3 minutes after the supine assessment is completed. Body temperature and respiratory rate will be measured only during the supine assessment.
4. For *de novo* subjects, premenopausal women of childbearing potential must have a negative serum pregnancy test within 21 days before Baseline. Urine pregnancy testing will be performed for all female subjects at the other visits as noted.
5. The TNmAS-MAL assessment will be performed prior to any scheduled laboratory draws. The most affected limb will be determined by the investigator.
6. At the end of treatment, a 2-week taper period will take place from Weeks 54 to 56. Subjects who discontinue early should also follow the 2-week taper period.

Figure 1: Timeline Diagram, Study OS440-3005

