- Collect unused study medication, assess compliance, and study drug accountability ([Section 7.9](#)).
- Record any AEs that have occurred ([Section 9.7](#)).
- Record all concomitant medications/therapies the subject is currently taking ([Section 7.7](#)).
- Schedule the next study visit.

6.5 Visit 7 End of Taper (Telephone Visit) – Week 56

- Record any AEs that have occurred ([Section 9.7](#)).
- Record all concomitant medications/therapies the subject is currently taking ([Section 7.7](#)).
- Schedule the final study visit.

6.6 Visit 8 (Final Visit or Early Termination) – Week 60

The assessments/procedures listed for Visit 8 (Final Visit) are to be completed by all subjects regardless of whether they complete the entire study or prematurely withdraw from the study. If the Final Visit is performed before Week 60 due to early termination of the subject, every effort should be made to perform the clinical evaluations as follows, especially blood sampling for hematology and serum chemistry, urinalysis, ECG, and the 2-week study drug taper. Assessments/procedures will include the following:

- Record weight ([Section 9.4](#)).

- Record vital sign measurements, including BP, heart rate, respiratory rate, and body temperature (Section 9.2).
- Collect blood and urine samples for hematology, serum chemistry, and urinalysis (Section 9.5). Subject should be fasting if possible.
- Perform a standard 12-lead ECG (Section 9.6.1).
- Collect a urine sample for pregnancy testing for women of childbearing potential (Section 7.8).
- Administer the C-SSRS (Section 9.6.3).
- Perform the TNmAS-MAL assessment (Section 8.2).
- Administer the EDSS assessment (Section 8.3).
- Administer the PGIC questionnaire (Section 8.1).
- Administer the USP questionnaire (Section 9.6.2).
- Collect unused study medication, assess compliance, and study drug accountability (Section 7.9).
- Record any AEs that have occurred (Section 9.7).
- Record all concomitant medications/therapies the subject is currently taking (Section 7.7).

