7.5 Selection and Timing of Doses in the Study

There will be a 9-day titration period (3 days at 40 mg/day, 3 days at 60 mg/day, and 3 days at 80 mg/day), then a 1-year maintenance period, followed by a 2-week taper period. The maintenance dose will be the highest tolerated dose, not exceeding 80 mg per day. Subjects who discontinue early should also follow the 2-week taper period. Figure 2 presents the dosing regimen flowchart, including titration and taper, to be used during the study.

Figure 2: Flowchart of Open-Label Dosing Regimen, Study OS440-3005

At the end of treatment, a 2-week taper period will take place from Weeks 54 to 56. Subjects who discontinue early should also follow the 2-week taper period.

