12.4 Withdrawal of Subjects

Withdrawn subjects are those who do not complete all evaluations and procedures outlined in the protocol. Subject withdrawal requires a 2-week dose taper. A subject will be considered to have discontinued prematurely if he/she withdraws prior to completing Visit 8 (Final Visit). If a subject misses 7 consecutive days AND has taken less than 80% of their doses of study medication in a 42-day (6-week) period, then the subject must be discontinued. Subjects may also be withdrawn from the study because of any of the following:

- **Adverse Event:** An AE that, in the opinion of the investigator or Sponsor, suggests that continued participation in the study is not in the subject's best interest for safety reasons (also see [Section 10](#)). All AEs that are present when the subject withdraws from the study will be followed as described in [Section 9.7.4](#).
- **Medical Condition:** Any medical condition that, in the investigator's judgment, would increase the risk or interfere with the evaluation of study objectives.
- **Lost to Follow-up:** Confirmed at minimum by two phone calls and a traceable letter without answer.
- **Subject Request:** Subject requests for any reason to be withdrawn or withdraws his/her consent. Every effort should be made to determine the reason for the withdrawal request (e.g., AE, lack of efficacy, scheduling issues, etc.).
- **Protocol Deviation:** A subject may be withdrawn from the study at the discretion of the investigator or Sponsor due to poor compliance with protocol requirements that may compromise the study results or subject safety.
- **Enrollment in Another Study:** Enrollment in other protocols involving research drugs, medical devices, or surgeries.
- **Other Anti-spasticity Treatment:** Starting any other pharmacological anti-spasticity treatment during the study.

- **Relapse:** Subjects who experience an acute MS exacerbation/relapse (symptoms including but not limited to visual disturbance, dizziness, tingling, or extreme fatigue lasting greater than 24 hours and occurring at least 30 days after a previous relapse) requiring immediate therapy or adjustment in disease-modifying medication dose (e.g., oral or intravenous high-dose steroid therapy).

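### For early terminators, SAP 7.3.3 places end-of-taper or off-drug values at on-treatment visits with no flag, on the better-supported reading that Visit 8 follows the taper

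*Protocol*

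**What the plan says.** **Early termination, protocol.** Table 1 footnote 2 tells a withdrawing subject to taper and says that "all evaluations described under Visit 8/Week 60 (Final Visit) must be performed". Footnote 6 adds: "Subjects who discontinue early should also follow the 2-week taper period". Section 12.4 states: "Subject withdrawal requires a 2-week dose taper". Section 6.6, on a Final Visit held before Week 60, asks for every effort to complete the evaluations, "especially blood sampling for hematology and serum chemistry, urinalysis, ECG, and the 2-week study drug taper". None of these gives an order or an interval. Section 7.5 says "Figure 2 presents the dosing regimen flowchart, including titration and taper, to be used during the study", but that figure is not shown, nor is the timeline in Figure 1.

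**Completers, protocol.** The taper runs from Week 54 to Week 56. The Week 56 telephone visit in Section 6.5 includes the item "Schedule the final study visit", and Visit 8 follows at Week 60. Visit 8 has the item "Collect unused study medication, assess compliance, and study drug accountability" and no dispensing item.

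**SAP.** Section 7.3.3 sends early-termination data to the nearest scheduled visit or, if that visit already holds valid data, to the next one available. It mentions neither last dose nor taper. Sections 9.2, 10.3, 10.4 and 10.6 summarise TNmAS, EDSS, labs, vital signs, USP and ECG by visit or time point. Section 7.4.1 presents tables by modal dose.

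**The concern.** Long-term safety is the primary objective, and the descriptive tables by visit are how most of the safety measurements will be read. If Visit 8 follows the taper, an early terminator's labs, vital signs, ECG and USP come from a subject who is finishing reduced dosing or is off drug. SAP 7.3.3 nevertheless gives those values the label of a maintenance visit. A value obtained off drug could then stand in the 80 mg modal-dose column at Week 28. Week 28 matters most for ECG, TNmAS-MAL and EDSS, because it is their only scheduled on-treatment assessment after baseline. The subjects concerned are those who stopped early, often the ones a safety reader most wants to see correctly labelled.

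**Working it through.** **Step 1. Which order does the text favour?** Three cues point to taper first. Footnote 2 names the taper before the evaluations. For completers the final visit is scheduled at the end-of-taper call. Visit 8 takes drug back and dispenses none. Section 6.6 points weakly the other way by listing the taper after the blood samples and ECG. Taper first is therefore an inference, though the better-supported one.

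**Step 2. Inputs, from protocol Table 1.**
- Taper: (56 − 54) × 7 = 14 days.
- Completers' interval from end of taper to Visit 8: 60 − 56 = 4 weeks.
- Labs: Weeks 6, 14, 28, 42, 54, 60. Vital signs and USP: the same plus Week 2.
- ECG, TNmAS-MAL and EDSS: Weeks 28 and 60.

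Let w be the week the taper starts, w < 54. Visit 8 falls at w + 2 (end of taper) or at w + 6 (4 weeks later, as for completers). I assume that earlier visits were attended on schedule.

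**Step 3. Labs, vital signs and USP.** The last on-treatment visit is Week 54 and the next scheduled one is Week 60; their midpoint is 57.
- Visit 8 at w + 2: w + 2 < 57 gives w < 55, so every taper started before Week 54 lands on an on-treatment visit.
- Visit 8 at w + 6: w + 6 < 57 gives w < 51.

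SAP Table 1, as it reads in the available text, also marks these assessments at the Week 56 telephone visit. If that visit counts, the midpoint is 55 and the limits become w < 53 and w < 49.

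**Step 4. ECG, TNmAS and EDSS.** SAP 7.3.3 does not say whether the nearest visit must be one that schedules the assessment.
- Only such visits count: w < 28 goes to Week 28, still empty. For w ≥ 28, Week 28 already holds data or Week 60 is nearer, so the value goes to Week 60, which is off drug for completers too.
- Any visit counts: most values go to an on-treatment visit.

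**Step 5. Examples, Visit 8 at w + 2.**

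| Taper starts (week) | Visit 8 (week) | Labs go to | ECG, only ECG visits | ECG, any visit |
|---|---|---|---|---|
| 5 | 7 | 6 | 28 | 6 |
| 20 | 22 | 28 | 28 | 28 |
| 29 | 31 | 42 (28 is filled) | 60 | 42 |
| 45 | 47 | 54 (42 is filled) | 60 | 42 |
| 52 | 54 | 54 | 60 | 54 |

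**Step 6. Share of stop times.** Stop times from Week 1 to Week 53.5 were taken in steps of 0.1 week with equal weight, which is an assumption. The ranges for labs and USP span both readings of the nearest visit.

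| Placed at an on-treatment visit | Visit 8 at w + 2 | Visit 8 at w + 6 |
|---|---|---|
| Labs, USP | 99% to 100% | 91% to 95% |
| ECG, only ECG visits | 51% (270/526) | 51% |
| ECG, any visit | 99% | 91% |

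Vital signs share the USP schedule, and TNmAS-MAL and EDSS share the ECG schedule. These are shares of possible stop times, not of subjects.

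**Step 7. USP recall.** The questionnaire covers the past 4 weeks (protocol 9.6.2). At w + 2 that is 2 weeks of pre-taper dosing and 2 weeks of taper, so the distortion is partial. At w + 6 the window runs from w + 2 to w + 6, all after the taper.

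**The case against.** **The sequence may be in the figures.** Figures 1 and 2 are cited for timeline and taper and cannot be seen here. This stands, so the absence of a sentence on order is not treated as a defect in itself. If the figures put Visit 8 before the taper, placing its values at on-treatment visits is correct and the mapping problem disappears.

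**A value at the end of the taper is not plainly off treatment.** This also stands. At w + 2 the subject is only just finishing reduced doses. That is a reason for three dosing classes rather than two; it does not justify a full-dose label.

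**The core safety analysis is untouched.** Largely true. SAP 10.1 defines TEAEs by dose dates and tabulates them by dose at the event and by period, so this rule does not move them. No tests are planned, full listings are kept, and the assignment can be corrected later from dosing dates. The by-visit tables would still mislead as specified.

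**Stronger readings that the documents do not support.** A reader might infer that adverse events during an early terminator's taper go uncollected. Under taper first, Visit 8 asks about everything since the last contact (protocol 9.7.1), so all 14 taper days are covered. Only a site that held Visit 8 first would have 0 of 14 days covered by a scheduled contact. Even then, the 30-day awareness rule and 24-hour SAE rule (9.7.3) and the supervision of clinically significant events (9.7.4) give partial cover. A reader might also infer that every early terminator's ECG from a taper begun before Week 28 lands at Week 28. That needs the assessment-specific reading of SAP 7.3.3 and a Visit 8 that took place.

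**Conclusion.** The concern holds as a minor point about SAP 7.3.3. On the better-supported order, the rule puts end-of-taper or off-drug values into on-treatment summaries for labs, vital signs and USP in nearly all tapers started before Week 54, or before about Week 51 if Visit 8 comes 4 weeks after the taper. For ECG, TNmAS and EDSS the extent depends on a reading that the SAP leaves open: tapers begun before Week 28 on the narrow one, most tapers on the wide one.

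This rests on taper first, a 14-day taper and attendance on schedule. Whether subjects who only ever reached 40 mg taper on withdrawal is unsettled: protocol 7.1.1 exempts them, while 12.4 and footnote 6 make no exception. The documents give no early-termination rate, so the number of subjects affected cannot be stated. No inference is affected.

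**What to change.** **Main change, SAP 7.3.3.** Use dosing and visit dates to classify every early-termination assessment (labs, vital signs, ECG, USP, TNmAS-MAL and TNmAS-TL, EDSS) as on full dose, during taper or after last dose. Keep the last two classes out of the on-treatment visit summaries and report them in a separate early-termination/post-taper row. SAP 8.6 already lists the dosing dates needed.

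**Secondary clarification, protocol footnote 2 and Sections 6.6 and 12.4.** State that Visit 8 follows the taper. Where it has to be held earlier, make the existing Visit 7 call for adverse events and concomitant medication at the end of the taper. Say at the same time whether 40 mg-only subjects taper on withdrawal.

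**Cost.** Amendment wording, one derived variable and an occasional extra call. The on-treatment summaries will hold slightly fewer values. Some subjects will not answer the call, and those lost to follow-up will still be missed.

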6.1 Screening – *De Novo* Subjects Only

For *de novo* subjects being considered for enrollment, a Screening visit (shown in Table 1) should occur a maximum of 21 days prior to Baseline to allow for any concomitant medication wash-out required for Inclusion Criterion 6. For *de novo* subjects, the following procedures will be done at this Screening visit:

- Obtain a signed and dated ICF from each subject prior to any study-specific procedures being conducted (Section 13.3).
- Assess eligibility according to the inclusion (Section 5.1) and exclusion criteria (Section 5.2).
- After establishing the subject's eligibility to participate, explain to *de novo* subjects how to withdraw all anti-spasticity medication (up to a 21-day period) prior to the next visit.
- Record demographic data, including age, sex, race, and ethnicity.
- Record medical and surgical history (Section 9.1).
- Record physical examination results (Section 9.3).
- Record weight and height (Section 9.4).
- Record vital sign measurements, including blood pressure (BP), heart rate, respiratory rate, and body temperature (Section 9.2).
- Collect blood and urine samples for hematology, serum chemistry, and urinalysis (Section 9.5). Subject should be fasting if possible.
- Perform a standard 12-lead electrocardiogram (ECG) (Section 9.6.1).
- Collect a sample to perform a serum pregnancy test (Section 7.8).
- Administer the Columbia–Suicide Severity Rating Scale (C-SSRS) (Section 9.6.3).
- Perform the TNmAS-MAL assessment (Section 8.2).
- Administer the EDSS assessment (Section 8.3).
- Administer the USP questionnaire (Section 9.6.2).
- Record all concomitant medications/therapies the subject is currently taking (Section 7.7).

6.2 Baseline – Visit 6 (Final Visit) of Study OS440-3004 (Week 0)

For *de novo* subjects, the following assessments and procedures will be performed at the Baseline visit: assign enrollment number, vital signs, urine pregnancy test, C-SSRS, TNmAS-MAL, PGIC,

USP, dispensing of study medication, recording of AEs and concomitant medications, and scheduling/confirmation of the next study visit.

For Study OS440-3004 subjects willing to continue into this study, Baseline for this study will be conducted at the same time as Visit 6/Day 92 (Final Visit) of Study OS440-3004. All assessments performed at Visit 6/Day 92 (Final Visit) of Study OS440-3004 should not be repeated but should be recorded as the same assessments at Baseline for this study.

At Baseline, the investigator will fully explain to the subject the objectives, characteristics, and procedures for the open-label study. Baseline assessments/procedures will include the following:

- Obtain a signed and dated ICF from each subject prior to any study-specific procedures being conducted ([Section 13.3](#)).
- Assess eligibility according to the inclusion ([Section 5.1](#)) and exclusion criteria ([Section 5.2](#)).
- Assignment of an enrollment number ([Section 7.4](#)).
- Record demographic data, including age, sex, race, and ethnicity.
- Record medical and surgical history ([Section 9.1](#)).
- Record physical examination results ([Section 9.3](#)).
- Record weight and height ([Section 9.4](#)).
- Record vital sign measurements, including blood pressure (BP), heart rate, respiratory rate, and body temperature ([Section 9.2](#)).
- Collect blood and urine samples for hematology, serum chemistry, and urinalysis ([Section 9.5](#)). Subject should be fasting if possible.
- Perform a standard 12-lead electrocardiogram (ECG) ([Section 9.6.1](#)).
- Because contraception is required throughout the study for both males and females, the use of an acceptable method throughout the study will be discussed with all subjects ([Section 7.8](#)).
- Collect a urine sample for pregnancy testing for women of childbearing potential ([Section 7.8](#)).
- Administer the Columbia–Suicide Severity Rating Scale (C-SSRS) ([Section 9.6.3](#)).
- Perform the TNmAS-MAL assessment ([Section 8.2](#)).
- Administer the EDSS assessment ([Section 8.3](#)).
- Administer the PGIC questionnaire ([Section 8.1](#)).
- Administer the USP questionnaire ([Section 9.6.2](#)).

- Dispense the study medication. The investigator will explain to the subject how to take the study medication and the regimen to be followed until the next visit ([Section 7.5](#)).
- The site will administer the first daily dose of study medication to the subject.
- Record any adverse events (AEs) that have occurred ([Section 9.7](#)).
- Record all concomitant medications/therapies the subject is currently taking ([Section 7.7](#)).
- Schedule the next study visit.

6.3 Visits 1, 2, 3, 5, and 6 – Weeks 2, 6, 14, 42, and 54

Assessments/procedures will include the following:

- Record vital sign measurements, including BP, heart rate, respiratory rate, and body temperature ([Section 9.2](#)).
- At Visits 2, 3, 5, and 6, collect blood and urine samples for hematology, serum chemistry, and urinalysis ([Section 9.5](#)). Subject should be fasting if possible.
- Collect a urine sample for pregnancy testing for women of childbearing potential ([Section 7.8](#)).
- Administer the C-SSRS ([Section 9.6.3](#)).
- Administer the USP questionnaire ([Section 9.6.2](#)).
- Dispense the study medication. The investigator will explain to the subject how to take the study medication and the regimen to be followed until the next visit ([Section 7.5](#)).
- Collect unused study medication, assess compliance, and study drug accountability ([Section 7.9](#)).
- Record any AEs that have occurred ([Section 9.7](#)).
- Record all concomitant medications/therapies the subject is currently taking ([Section 7.7](#)).
- Schedule the next study visit.

6.4 Visit 4 – Week 28

Assessments/procedures will include the following:

- Record weight ([Section 9.4](#)).

- Record vital sign measurements, including BP, heart rate, respiratory rate, and body temperature ([Section 9.2](#)).
- Collect blood and urine samples for hematology, serum chemistry, and urinalysis ([Section 9.5](#)). Subject should be fasting if possible.
- Perform a standard 12-lead ECG ([Section 9.6.1](#)).
- Collect a urine sample for pregnancy testing for women of childbearing potential ([Section 7.8](#)).
- Administer the C-SSRS ([Section 9.6.3](#)).
- Perform the TNmAS-MAL assessment ([Section 8.2](#)).
- Administer the EDSS assessment ([Section 8.3](#)).
- Administer the USP questionnaire ([Section 9.6.2](#)).
- Dispense the study medication. The investigator will explain to the subject how to take the study medication and the regimen to be followed until the next visit ([Section 7.5](#)).
- Collect unused study medication, assess compliance, and study drug accountability ([Section 7.9](#)).
- Record any AEs that have occurred ([Section 9.7](#)).
- Record all concomitant medications/therapies the subject is currently taking ([Section 7.7](#)).
- Schedule the next study visit.

6.5 Visit 7 End of Taper (Telephone Visit) – Week 56

- Record any AEs that have occurred ([Section 9.7](#)).
- Record all concomitant medications/therapies the subject is currently taking ([Section 7.7](#)).
- Schedule the final study visit.

6.6 Visit 8 (Final Visit or Early Termination) – Week 60

The assessments/procedures listed for Visit 8 (Final Visit) are to be completed by all subjects regardless of whether they complete the entire study or prematurely withdraw from the study. If the Final Visit is performed before Week 60 due to early termination of the subject, every effort should be made to perform the clinical evaluations as follows, especially blood sampling for hematology and serum chemistry, urinalysis, ECG, and the 2-week study drug taper. Assessments/procedures will include the following:

- Record weight ([Section 9.4](#)).

- Record vital sign measurements, including BP, heart rate, respiratory rate, and body temperature (Section 9.2).
- Collect blood and urine samples for hematology, serum chemistry, and urinalysis (Section 9.5). Subject should be fasting if possible.
- Perform a standard 12-lead ECG (Section 9.6.1).
- Collect a urine sample for pregnancy testing for women of childbearing potential (Section 7.8).
- Administer the C-SSRS (Section 9.6.3).
- Perform the TNmAS-MAL assessment (Section 8.2).
- Administer the EDSS assessment (Section 8.3).
- Administer the PGIC questionnaire (Section 8.1).
- Administer the USP questionnaire (Section 9.6.2).
- Collect unused study medication, assess compliance, and study drug accountability (Section 7.9).
- Record any AEs that have occurred (Section 9.7).
- Record all concomitant medications/therapies the subject is currently taking (Section 7.7).

